## **5. INVESTIGATIONAL MEDICINAL PRODUCTS**

### **5.1. Randomization and Treatment Codes**

The randomization will be performed via an Interactive Web Response System (IWRS), whereby study treatment will be assigned to subjects according to the randomization schedule. A unique subject number will be provided during randomization. Groups 1 and 2 will be randomized in a 3:1 ratio to receive either GS-9992 and TAF or TAF alone. Groups 3 and 5 will be enrolled based on HBeAg status and receive GS-9992 and TAF. Group 4 will be enrolled based on HBeAg status and receive GS-9992.

### **5.2. Description and Handling of GS-9992 and TAF**

#### **5.2.1. Formulation**

##### **5.2.1.1. GS-9992**

GS-9992 is provided in capsule formulation containing 25 mg strengths. The current composition of the capsules includes Active Pharmaceutical Ingredient (API) GS-9992 and the following excipients: lactose and sodium stearyl fumarate.

GS-9992 tablets, 100 mg, are blue, round, film-coated tablets. In addition to the active ingredient, each film-coated tablet contains the following ingredients: lactose anhydrous, microcrystalline cellulose, croscarmellose sodium, hydroxypropylcellulose, sodium stearyl fumarate, colloidal silicon dioxide, polyvinyl alcohol, polyethylene glycol, titanium dioxide, talc, Fd&C Blue #1/Brilliant Blue FcF aluminum lake, and Fd&C Blue #2 Indigo Carmine aluminum lake.

GS-9992 tablets, 200 mg, are blue, oval, modified capsule shape, film-coated tablets. In addition to the active ingredient, each film-coated tablet contains the following ingredients: lactose anhydrous, microcrystalline cellulose, croscarmellose sodium, hydroxypropylcellulose, sodium stearyl fumarate, colloidal silicon dioxide, polyvinyl alcohol, polyethylene glycol, titanium dioxide, talc, Fd&C Blue #1/Brilliant Blue FcF aluminum lake, and Fd&C Blue #2 Indigo Carmine aluminum lake.

##### **5.2.1.2. Tenofovir Alafenamide [TAF] Tablets**

TAF 25 mg tablets contain 28 mg of tenofovir alafenamide fumarate, which is equivalent to 25 mg of tenofovir alafenamide. The tablets are yellow, round-shaped, and film-coated. The tablets are debossed with “GSI” on one side and “25” on the other side. In addition to the active ingredient, each film-coated tablet contains the following inactive ingredients: lactose monohydrate, microcrystalline cellulose, croscarmellose sodium, magnesium stearate, polyethylene glycol, polyvinyl alcohol, talc, titanium dioxide, and yellow iron oxide.

## **5.2.2. Packaging and Labeling**

### **5.2.2.1. GS-9992**

GS-9992 capsules, 25 mg are packaged in white, high density polyethylene (HDPE) bottles. Each bottle contains 17 capsules, silica gel desiccant and packing material. Each bottle is enclosed with a white, continuous thread, child-resistant polypropylene screw cap with an induction-sealed and aluminum-faced liner.

GS-9992 tablets, 100 mg are packaged in white, high density polyethylene (HDPE) bottles. Each bottle contains 17 tablets, silica gel desiccant and packing material. Each bottle is enclosed with a white, continuous thread, child-resistant polypropylene screw cap with an induction-sealed and aluminum-faced liner.

GS-9992 tablets, 200 mg are packaged in white, high density polyethylene (HDPE) bottles. Each bottle contains 35 tablets, silica gel desiccant and packing material. Each bottle is enclosed with a white, continuous thread, child-resistant polypropylene screw cap with an induction-sealed and aluminum-faced liner.

Study drug to be distributed to centers in the US and other participating countries shall be labeled to meet applicable requirements of the FDA, EU Guideline to Good Manufacturing Practice–Annex 13 (Investigational Medicinal Products), and/or other local regulations.

### **5.2.2.2. TAF**

TAF tablets are packaged in white, high density polyethylene (HDPE) bottles. Each bottle contains 30 tablets, silica gel desiccant and polyester packing material. Each bottle is enclosed with a white, continuous thread, child-resistant polypropylene screw cap with an induction-sealed and aluminum-faced liner.

Study drug to be distributed to centers in the US and other participating countries shall be labeled to meet applicable requirements of the FDA, EU Guideline to Good Manufacturing Practice–Annex 13 (Investigational Medicinal Products), and/or other local regulations.

## **5.2.3. Storage and Handling**

### **GS-9992**

GS-9992 capsules, 25 mg, GS-9992 tablets, 100 mg and GS-9992 tablets, 200mg, should be stored at 2°C to 8°C (36°F to 46°F). Storage conditions are specified on the label. Until dispensed to the subjects, all bottles of study drugs should be stored in a securely locked area, accessible only to authorized site personnel.

To ensure the stability and proper identification, study drug(s) should not be stored in a container other than the container in which they were supplied.

Consideration should be given to handling, preparation, and disposal through measures that minimize drug contact with the body. Appropriate precautions should be followed to avoid direct eye contact or exposure when handling.

## **TAF**

TAF tablets should be stored at controlled room temperature of 25°C (77°F); excursions are permitted between 15°C and 30°C (59°F and 86°F). Storage conditions are specified on the label. Until dispensed to the subjects, all bottles of study drugs should be stored in a securely locked area, accessible only to authorized site personnel.

To ensure the stability and proper identification, study drug(s) should not be stored in a container other than the container in which they were supplied.

Consideration should be given to handling, preparation, and disposal through measures that minimize drug contact with the body. Appropriate precautions should be followed to avoid direct eye contact or exposure when handling.

### **5.3. Dosage and Administration of GS-9992 and TAF**

Study drug(s) are to be taken at the same time each day (i.e., 24 hour window between TAF doses and 24 hour window between GS-9992 doses, if applicable).

Groups 1 and 2: Subjects will be randomly assigned (3:1) the following treatments:

- Group 1 (n = 30): GS-9992 50 mg (2 × 25 mg capsules) once daily one hour before or one hour after a meal plus TAF 25 mg once daily with food for 12 weeks then TAF 25 mg once daily with food for 36 weeks.
- Group 2 (n = 10): TAF 25 mg once daily with food for 48 weeks

Groups 3,4, and 5 will be assigned:

- Group 3 (n = 30): GS-9992 200 mg (2 x 100 mg tablets) once daily one hour before or one hour after a meal plus TAF 25 mg once daily with food for 12 weeks then TAF 25 mg once daily with food for 36 weeks.
- Group 4 (n = 20): GS-9992 100 mg tablet once daily one hour before or one hour after a meal for 12 weeks. Subjects will remain on their current commercially available NUC(s) therapy for the duration of the study. All subjects will be followed through Week 48.
- Group 5 (n=30): GS-9992 400 mg (2 x 200 mg tablets) once daily one hour before or one hour after a meal plus TAF 25 mg once daily with food for 12 weeks then TAF 25 mg once daily with food for 36 weeks.

#### 5.4. Prior and Concomitant Medications

Concomitant/previous medications **taken within 30 days of screening**, up to and including the date of the last study visit, need to be recorded in the source documents and eCRFs.

The following medications are excluded while subjects are participating in the study. These medications are **prohibited during the screening period and for a minimum of 30 days prior to the Screening** visit through the end of treatment:

- Investigational agents or devices for any indication
- Nephrotoxic agents (e.g., aminoglycosides, amphoterecin B, vancomycin, cidofovir, foscarnet, cisplatin, pentamidine, cyclosporine, tacrolimus)
- Probenecid
- Agents that reduce renal function or compete for active tubular secretion with tenofovir (e.g., cidofovir, acyclovir, valacyclovir, ganciclovir, valganciclovir)
- Antiretroviral regimens that contain pharmacokinetic boosters (i.e. ritonavir or cobicistat) for the treatment of HIV.
- Concomitant use of certain medications or herbal/natural supplements (inducers of drug transporters i.e., P-gp and/or inhibitors of OATP 1B1/1B3) with study drug(s) may result in PK interactions.
- Systemic chemotherapeutic agents, systemic corticosteroids (except short-term use of prednisone as a steroid burst [ $\leq 1$  week of use]), immunosuppressant, or immunomodulating agents are prohibited for a minimum of 3 months prior to screening period and during the study.

**Examples of representative medications which are prohibited from 21 days prior to Day 1 through the end of treatment are listed below:**

**Table 5-1. Disallowed Concomitant Medications**

Medication Class	Prohibited Medications
Anticonvulsants	Carbamazepine, Oxcarbazepine, Phenobarbital, Phenytoin
Antimycobacterials	Rifapentine, Rifabutin, Rifampin
Hematopoietic Growth Factor*	Eltrombopag
Herbal/Natural Supplements	St. John's Wort, Echinacea, Milk thistle (i.e., silymarin), Chinese herb sho-saiko-to (or Xiao-Shai-Hu-Tang)
Lipid Regulating Agents*	Gemfibrozil

\* For subjects receiving GS-9992 in combination with TAF (Groups 1, 3 and 5 only)

Should subjects have a need to initiate treatment with any excluded concomitant medication, including herbal/natural products/therapies, and over the counter medications, the

Gilead Sciences Medical Monitor must be consulted prior to initiation of the new medication. In instances where an excluded medication is initiated prior to discussion with the Sponsor, the investigator must notify Gilead Sciences as soon as he/she is aware of the use of the excluded medication.

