#### **1.4. Rationale for This Study**

Given the low rate of HBsAg loss with currently available therapies and the treatment burden associated with life-long treatment to maintain viral suppression, there is a need to identify new therapies that may provide durable HBsAg loss with a finite treatment duration. The primary objective is to evaluate the safety, tolerability and efficacy of GS-9992 in association with an oral nucleotide (NUC) HBV polymerase inhibitor (TAF or other commercially available NUC) for the treatment of CHB subjects, while also evaluating the changes in HBV specific immune responses following treatment with GS-9992.

This Phase 2 study will be conducted in subjects with CHB, who are currently not receiving treatment for CHB (can be either treatment naïve or previously treated) or are virally-suppressed on a commercially available oral NUC. Viremic subjects with CHB generally have a rapid decline in viremia in response to beginning antiviral treatment. The decrease in viral burden may allow for an increased responsiveness to immune stimulation and forms the basis for the design of Groups 1-3 and 5 in this study. To further evaluate GS-9992 ability to improve immune response, an additional group, Group 4, will enroll virally-suppressed CHB subjects on a commercially available NUC. The immune responsiveness of CHB patients has been shown to improve in patients who are on chronic suppressive antiviral therapy with less antigen burden. Virally-suppressed patients will have lower levels of HBV virions and proteins, including HBsAg, within the serum as well as lower expression of HBV antigens within infected hepatocytes. Therefore Group 4 will evaluate the potential maximal efficacy benefits of GS-9992 in virally-suppressed CHB subjects.

Further, the safety data with GS-9992 in treatment naive subjects and in virally-suppressed subjects was evaluated in a Phase 1b study SBP-9200-101 and in the ongoing Phase 2 study SBP-9200-HBV-201. Both studies support the evaluation of GS-9992 in these populations. Subjects will be stratified by HBeAg status. HBeAg status has been shown in prior studies of TDF (GS-US-174-0102 and GS-US-174-0103) to be a predictor of eventual HBsAg loss with TDF treatment irrespective of HBV genotype.

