### 3.3. Study Treatments

Approximately 120 chronic, immune-active, HBV-infected adults without cirrhosis will be enrolled; including 100 viremic subjects not currently on HBV nucleos(t)ide (NUC) and 20 virally suppressed subjects on a commercially available NUC.

Approximately 40 viremic subjects will be randomized (3:1) to Group 1 and Group 2, below:

**Groups 1 and 2:** Subjects will be randomized (3:1) to the following:

- Group 1: Approximately 30 subjects will be administered GS-9992 50 mg (2 × 25 mg capsules) once daily one hour before or one hour after a meal plus TAF 25 mg once daily with food for 12 weeks then TAF 25 mg once daily with food for 36 weeks.
- Group 2: Approximately 10 subjects will be administered TAF 25 mg once daily with food for 48 weeks

Randomization will be stratified by HBeAg status (positive or negative) at screening with approximately 40% of HBeAg negative subjects enrolled.

**Group 3:** Approximately 30 viremic subjects will be administered GS-9992 200 mg (2 x 100 mg) once daily one hour before or one hour after a meal plus TAF 25 mg once daily with food for 12 weeks then TAF 25 mg once daily with food for 36 weeks.

Approximately 40% of subjects enrolled in Group 3 will be HBeAg negative.

**Group 4:** Approximately 20 virally suppressed subjects currently being treated with a commercially available NUC(s) for CHB will be administered GS-9992 100 mg tablet once daily one hour before or one hour after a meal for 12 weeks.

Approximately 50% of subjects enrolled in Group 4 will be HBeAg negative. Subjects will remain on their current commercially available NUC(s) therapy for the duration of the study. All subjects will be followed through Week 48.

**Group 5 (Hong Kong):** Approximately 30 viremic subjects may be enrolled and assigned:

GS-9992 400 mg (2 x 200 mg tablets) once daily one hour before or one hour after a meal plus TAF 25 mg once daily with food for 12 weeks then TAF 25 mg once daily with food for 36 weeks.

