#### **4.4. Group 4 Inclusion Criteria**

Subjects must meet all of the following inclusion criteria to be eligible for participation in this study:

- 1) Ability to understand and sign a written informed consent form, which must be obtained prior to initiation of study procedures.
- 2) Aged 18 to 70 years of age, inclusive, based on the date of screening visit.
- 3) Females of childbearing potential (as defined in [Appendix 4](#)) must have a negative serum pregnancy test at screening and a negative urine test at Baseline before dosing.
- 4) Male subjects and female subjects of childbearing potential who engage in heterosexual intercourse must agree to use protocol specified method(s) of contraception until 90 days after the last dose of GS-9992 and as described in [Appendix 4](#).

- 5) Documented evidence of chronic HBV infection (e.g. HBsAg positivity) for more than 6 months with detectable HBsAg at Screening.
- 6) Have at least one prior documented result of HBV DNA  $\leq$  lower limit of quantitation (LLOQ) from the local lab 6 or more months prior to Screening.
- 7) HBV DNA  $\leq$  20 IU/mL at Screening by Central Lab.
- 8) Have been on a commercially available HBV NUC treatment(s) (tenofovir alafenamide, tenofovir disoproxil fumarate, entecavir, adefovir, lamivudine, telbivudine, either as single agents or in combination) for less than 2 years, with no change in regimen for 3 months prior to screening.
- 9) Screening ECG without clinically significant abnormalities and with QTcF interval (QT corrected using Fridericia's formula)  $\leq$  450 msec for males and  $\leq$  470 msec for females.
- 10) Must be willing and able to comply with all study requirements.

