##### **3.1.2. Full Analysis Set**

The Full Analysis Set (FAS) includes all subjects who were randomized to Groups 1 or 2, or enrolled in Group 3-5, and who took at least 1 dose of any study drug. The study drugs in this study are GS-9992 and TAF. Subjects are grouped within FAS by treatment group to which they were randomized or enrolled.

This is the primary analysis set for efficacy analyses.

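### The Table 5-1 footnote exempts Group 4 from the eltrombopag and gemfibrozil prohibition, including Group 4 subjects whose background NUC is TAF, and gives no reason (minor)

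*Protocol*

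**What the plan says.** Table 5-1 in Protocol Section 5.4 lists the disallowed concomitant medications. The rows for eltrombopag and gemfibrozil carry an asterisk, and the footnote confines them: "For subjects receiving GS-9992 in combination with TAF (Groups 1, 3 and 5 only").

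Criterion 8 in Protocol Section 4.4 sets out the background therapy allowed in Group 4, with TAF first in the list: "Have been on a commercially available HBV NUC treatment(s) (tenofovir alafenamide, tenofovir disoproxil fumarate, entecavir, adefovir, lamivudine, telbivudine", alone or in combination. Section 3.3 keeps that therapy in place: "Subjects will remain on their current commercially available NUC(s) therapy for the duration of the study". Section 5.3 adds the investigational drug: "Group 4 (n = 20): GS-9992 100 mg tablet once daily one hour before or one hour after a meal for 12 weeks".

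Treatment assignment in Section 5.1 is worded differently for the groups. For two of the listed groups it says "Groups 3 and 5 will be enrolled based on HBeAg status and receive GS-9992 and TAF"; for the fourth it says "Group 4 will be enrolled based on HBeAg status and receive GS-9992".

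**The concern.** The footnote has two parts: a condition (GS-9992 taken together with TAF) and a closed list of groups. They agree only if no unlisted group takes the two drugs together, and Group 4 can. A Group 4 subject whose NUC is TAF meets the condition but is left out by the list.

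What is at stake is the consistency of a precaution. Group 4 exclusion criterion 12 refers to Section 5.4 for what is prohibited, and the text after Table 5-1 requires contact with the Medical Monitor before an excluded drug is started. Under the literal footnote neither safeguard is triggered by the two starred rows for a Group 4 subject on TAF, while both apply to a Group 1 subject on TAF and half the GS-9992 dose.

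**Working it through.** The plan gives no figure to reproduce. The check compares texts and then counts subjects.

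**Step 1: who takes GS-9992 together with TAF?** (Protocol Sections 3.3, 4.4 and 5.3)

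| Group | GS-9992, daily | TAF | Takes both? | In footnote list? |
|---|---|---|---|---|
| 1 | 50 mg | study drug | yes | yes |
| 2 | none | study drug | no | no |
| 3 | 200 mg | study drug | yes | yes |
| 4 | 100 mg | background, if that is the subject's NUC | yes, if on TAF | no |
| 5 | 400 mg | study drug | yes | yes |

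Condition and list agree in every row except Group 4.

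**Step 2: does anything in the table explain the exemption?**
- GS-9992 dose does not. Group 4 takes 100/50 = 2 times the Group 1 dose, and Group 1 is restricted.
- TAF dose does not obviously do so. The study dose is 25 mg, which Section 1.4.1 describes as the marketed dose for chronic hepatitis B.
- TAF alone is not the trigger, because Group 2 takes it and is not listed. The list fits a rule triggered by the two drugs together. This is an inference; the documents do not say why the rows are starred.

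**Step 3: does the rest of Section 5.4 close the gap?** The bullet on P-gp inducers and OATP 1B1/1B3 inhibitors has no group limit, and the table is introduced as a set of examples. The bullet names neither starred drug, so it does not clearly override a specific footnote that says 'only'. It also speaks of interactions with study drug. The SAP says "The study drugs in this study are GS-9992 and TAF", but in Group 4 the TAF is background therapy, and Protocol Section 6.3 requires accountability only for GS-9992 there.

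**Step 4: size, by planned numbers.**
- Given GS-9992: 30 + 30 + 20 + 30 = 110 of 120.
- Named in the footnote: 30 + 30 + 30 = 90, and 90/110 = 81.8%.
- Not named: 110 − 90 = 20, all in Group 4, and 20/110 = 18.2%.
- Of those 20, the number on TAF is not given. The range is 0 to 20, or 0% to 18.2% of subjects on GS-9992.
- Agents named in Table 5-1: 4 anticonvulsants + 3 antimycobacterials + 1 growth factor + 4 herbal products + 1 lipid agent = 13, of which 2 are starred.

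The 0 to 20 counts subjects who could take the combination outside the list. Those who would also use a starred drug are a subset whose size the documents do not give.

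**The case against.** The strongest reply is that the footnote is explicit. The word 'only' tells a site that the starred rows do not bind Group 4. The trial's usage also supports reading the GS-9992 and TAF combination as the name of an assigned regimen. SAP Section 7.1.5.1, for the 48-week analysis, labels subjects on GS-9992 and TAF as Groups 1, 3 and 5, and labels Group 4 separately as GS-9992 with commercially available NUC. SAP Section 7.2.3.1 does the same, and the objectives and Section 5.1 make a similar split. On that usage, condition and list match.

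Most of this stands. A reader might infer that a site cannot tell whether the two drugs are excluded for a Group 4 subject on TAF. The documents do not support that: taken at its word, the footnote says they are not. The line in Protocol Section 1.4, "in association with an oral nucleotide (NUC) HBV polymerase inhibitor (TAF or other commercially available NUC"), counts TAF among the NUCs, but it is background text and does not outweigh the operational sections.

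The reply explains how the wording probably arose. It does not explain why the precaution should stop there. The label follows who supplies the TAF, and no section says why that should matter for a co-medication rule.

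The reply is also right that no reason for the starred rows is given, so the documents cannot show that a Group 4 subject on TAF needs the restriction. Investigator discretion under Group 4 exclusion criterion 16 reduces the practical effect further.

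**Conclusion.** The point holds as a minor, low-severity inconsistency in a safety precaution. The literal rule exempts Group 4 subjects who may be taking the combination that the footnote describes, for 12 weeks and at twice the Group 1 dose of GS-9992, with no stated reason.

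It rests on two assumptions: that at least one Group 4 subject takes TAF, which criterion 8 permits but does not ensure, and that the restriction was prompted by taking the two drugs together, which fits the group list but is not stated.

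A reader might go further and infer a demonstrated hazard. The documents do not support that. They give no interaction data for either starred drug with this combination, and the number of subjects affected is unknown and probably very few. No efficacy analysis uses the footnote, and SAP Section 8 says that no pharmacokinetic analysis will be done. SAP Section 6.4 records that development of GS-9992 has stopped, so the edit matters for any dosing still to come or for reuse of this text elsewhere.

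**What to change.** Keep the footnote's condition and change the parenthesis to name Groups 1, 3 and 5, and Group 4 subjects whose NUC is TAF. Group 4 exclusion criterion 12 and the Medical Monitor requirement then apply to those subjects without further edits. If the sponsor has a documented reason to exempt Group 4, stating it in the footnote would also remove the inconsistency.

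The cost is one line of protocol text and one extra medication check for Group 4 subjects on TAF. A candidate who takes either drug might have to stop it or be excluded. Sample size, endpoints and analyses are unchanged.

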## **5.5. Accountability for GS-9992 and TAF**

The investigator is responsible for ensuring adequate accountability of all used and unused IMP capsules. This includes acknowledgement of receipt of each shipment of IMP (quantity and condition of capsules and/or tablets). All used and unused IMP capsules and/or tablets dispensed to subjects must be returned to the site.

GS-9992 and TAF accountability records will be provided to each study site to:

- Record the date received and quantity of IMP kits.
- Record the date, subject number and the IMP kit number dispensed.
- Record the date, quantity of used and unused IMP capsules and/or tablets, along with the initials of the person recording the information.

